16.6 SAFETY ANALYSIS

The evaluation of safety shall be carried out using the entire population (FAS) of data, making focus on adverse events (AE).

As primary safety objective, the incidence of adverse events and adverse reactions will be evaluated after 12 and 24 weeks of treatment, comparing patients treated with HEMAX PFS versus those treated with EPREX/ ERYPO®.

An AE shall be considered as treatment - emergent adverse event (TEAE), if it presents after the first dose administered of the investigational product or if, preexistent prior to the administration of the first dose, it worsens after the administration of the same.

All TEAEs will be presented summarized through the use of Tables, for each organ class and preferred term to denominate them. The Tables will present the number of patients for which events occurred, and the incidence rate, expressed as a percentage calculated on the number of patients from the entire population included in the safety FAS.

The TEAEs will be presented by causality (relationship with the study drug), intensity (mild, moderate, severe). Treatment - emergent events that are serious and that lead to treatment discontinuation will also be summarized using the preferred term and the class organ system involved.

In addition, and with focus on safety, the following will be discussed:

- Incidence of **thromboembolic events** (myocardial infarction, cerebrovascular accident, deep vein thrombosis and other thromboembolic events).

- Incidence of **hypertension** as TEAE.
- **Blood pressure** values at each visit.
- **Complete baseline laboratory data** and at week 12 and 24 visits,
- **Antibody dosages**, baseline and at weeks 12 and 24.

For safety analysis, descriptive statistics will be performed mainly to evaluate the incidence of adverse events and adverse reactions after 12 and 24 weeks of treatment and x2 test will be performed to compare the incidence of adverse events and adverse reactions of patients treated with HEMAX® PFS versus those treated with EPREX/ERYPO®.

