6 STUDY OBJECTIVES

The study has as a general objective the evaluation of the efficacy and safety of HEMAX PFS compared with EPREX/ ERYPO®, following a dose titration and maintenance scheme similar to that used in the clinical practice in our country, being the specific objectives the following.

6.1 PRIMARY OBJECTIVES:

Evaluate the efficacy of treatment with epoetin alfa through increased levels of hemoglobin from baseline value to the mean value of the 8 to 12 weeks of treatment, comparing patients treated with HEMAX PFS versus those treated with EPREX/ ERYPO®.

Evaluate the safety through the incidence of adverse events and adverse reactions after 12 and 24 weeks of treatment, comparing patients treated with HEMAX PFS versus those treated with EPREX/ ERYPO®.

6.2 SECONDARY OBJECTIVES:

Evaluate the efficacy of treatment with epoetin alfa through the percentage of responder patients (increase of Hb \geq 1g/ dl) after 12 weeks of treatment, comparing patients treated with HEMAX PFS versus those treated with EPREX/ ERYPO®.

Evaluate the percentage of transfusion requirement after 12 weeks of treatment, comparing patients treated with HEMAX® PFS versus those treated with EPREX/ ERYPO®.

Evaluate the intragroup efficacy (HEMAX® PFS and EPREX/ ERYPO®) of treatment with epoetin alfa through increased levels of hemoglobin from baseline in each one of the intermediate visits until the week 12 visit.

Evaluate the intragroup efficacy (HEMAX® PFS and EPREX/ ERYPO®) of the change from the twice - a - week dosing during the titration phase to a weekly dosing during the maintenance phase through the variation of the hemoglobin levels from week 12 to weeks 16, 20 and 24.

In addition, at week 12 and 24 visits, an anti - erythropoietin antibody dosing will be performed to evaluate treatment immunogenicity.

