16 STATISTICAL METHODOLOGY

16.1 SAMPLE SIZE JUSTIFICATION

A total N of 120 patients (60 in each group) will allow, with 80% of power, to rule out a difference between treatment groups greater than 1g/ dl in hemoglobin increase from baseline value to the mean value of the visits between week 8 and 12.

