16.5 EFFICACY ANALYSIS

The efficacy analysis will be performed for both FAS and PP populations. Descriptive statistics and inferential statistics will be performed through intergroup analysis (ANCOVA covariance analysis)-comparing each treatment group (patients treated with HEMAX PFS versus those treated with EPREX/ERYPO®) and an additional intragroup analysis analyzing the variations in hemoglobin (increase from baseline to the average of the visits between weeks 8 and 12) adjusted for the baseline value, using a significance level of 5%. Statistical analysis will be performed with SPSS software or equivalent.

The following parameters will be evaluated for treatment efficacy, according to the objectives defined by the protocol.

The **primary efficacy assessment** will be carried out through the levels of hemoglobin increase from baseline value to the mean value of the visits between week 8 and 12, comparing patients treated with HEMAX PFS versus those treated with EPREX/ERYPO®.

Additionally, **treatment equivalence** will be established if the difference between the two groups excludes a difference between treatment groups greater than 1g/ dl in hemoglobin increase from baseline value to the mean value of the visits between week 8 and 12 with a difference in the mean dose of epoetin alfa in these visits no greater than 20%.

The **secondary efficacy assessment** will be carried out through the evaluation of the following objectives:

- Percentage of responder patients (increase of Hb \geq 1g/ dl) after 12 weeks of treatment, comparing patients treated with HEMAX PFS versus those treated with EPREX/ERYPO®.

- Percentage of transfusion requirement after 12 weeks of treatment, comparing patients treated with HEMAX PFS versus those treated with EPREX/ ERYPO®.
- Intragroup efficacy (HEMAX PFS and EPREX/ ERYPO®) of treatment with Epoetin Alfa through increased levels of hemoglobin from baseline in each one of the intermediate visits until the week 12 visit.
- Evaluate the intragroup efficacy (HEMAX PFS and EPREX/ ERYPO®) of the change from the twice - a - week dosing during the titration phase to a weekly dosing during the maintenance phase through the variation of the hemoglobin levels from week 12 to the weeks 16, 20 and 24.

For **missing hemoglobin data**, the last observation carried forward method will be used.

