The trial starting date was February 15th, 2017 and the first patient was included on February 21st, 2018 and the date in which the last patient reached the primary evaluation criterion was March 23rd, 2021. Since the study started, the recruiting rate was lower than that expected. Many participating centers included one single patient or no one. During the whole study, Biosidus made its best effort to support and accompany the recruitment in the centers. Furthermore, new centers were opened until a total of 16 centers in CABA and Buenos Aires Province were achieved. Besides, amendments to the protocol were performed to include a specialized center in Paraguay.

Since in March 2020, an emergency situation was decreed due to COVID-19 pandemic. On March 20th, 2020, the Argentine National Administration for Drugs, Food, and Medical Devices (ANMAT) issued a set of regulations and recommendations, in a document titled "Regulations and recommendations regarding clinical pharmacology studies during the COVID-19 pandemic", in order to preserve the activities regarding the clinical pharmacology studies, protecting the safety and welfare of the study participants. As a consequence, and according to the clauses, Biosidus S.A. designed a risk mitigation plan (Annex 14.13), that was submitted to the Study Ethics Committees and to ANMAT.

Although the recruiting was not suspended, the health situation determined a reduction in the recruitment ratio. The interim analysis according to the obtained data showed, preliminary, that the results were those expected and allowed the conclusions of this report to be valid enough statistically, though the "n" was lower than that estimated at the beginning.

Considering that the studied population is a population at risk, and that the internal analysis gave consistent results, the recruitment was ended before achieving the 120-patient-target, and finally the study enrolled 43 patients (23 in HEMAX group, and 20 in Eprex/ Erypo® group)..

Thus, the population safety was considered as a priority, and, moreover, the integrity of the results, already collected, were kept.

6 General Considerations

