9.1 Adverse Events

As safety objective, the incidence of adverse events and adverse reactions will be evaluated after 12 and 24 weeks of treatment, comparing patients treated with HEMAX PFS versus those treated with EPREX/ ERYPO®.

An AE shall be considered as treatment - emergent adverse event (TEAE), if it presents after the first dose administered of the investigational product or if, preexistent prior to the administration of the first dose, it worsens after the administration of the same.

All TEAEs will be presented summarized through the use of Tables, for each organ class and preferred term to denominate them. The Tables will present the number of patients for which events occurred, and the incidence rate, expressed as a percentage calculated on the number of patients from the entire population included in the safety FAS.

The TEAEs will be presented by causality (relationship with the study drug), intensity (mild, moderate, severe). Treatment - emergent events that are serious and that lead to treatment discontinuation will also be summarized using the preferred term and the class organ system involved.

In addition, and with focus on safety, the following will be discussed:

- Incidence of thromboembolic events (myocardial infarction, cerebrovascular accident, deep vein thrombosis and other thromboembolic events).
- Incidence of hypertension as TEAE.
- Blood pressure values at each visit.
- Complete baseline laboratory data and at week 12 and 24 visits,
- Antibody dosages, baseline and at weeks 12 and 24.

For safety analysis, descriptive statistics will be performed mainly to evaluate the incidence of adverse events and adverse reactions after 12 and 24 weeks of treatment.

When calculating the incidence of adverse events, or any sub-classification (e.g. by treatment) each subject will be counted all the times a repetitions of adverse events will be occurred and the denominator will be the total population size.

All the adverse events occurred during the study will be listed according to treatment group and severity. The frequency of adverse events by system and treatment group, expressed as amount of events/number of affected patients and the relationship with study drug will be summarized.

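### The primary safety comparison has no planned effect estimate or interval: the protocol names only a chi-square test at an unstated level, and the SAP drops even that

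*Protocol*

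**What the plan says.** Protocol 6.1 lists two primary objectives. The second is to "Evaluate the safety through the incidence of adverse events and adverse reactions after 12 and 24 weeks of treatment", comparing the two products. Protocol 16.6 repeats it: "As primary safety objective, the incidence of adverse events and adverse reactions will be evaluated after 12 and 24 weeks of treatment".

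For method, Protocol 16.6 relies mainly on descriptive statistics and adds that a "x2 test will be performed to compare the incidence of adverse events and adverse reactions". It gives no significance level, margin, effect measure, confidence interval or rule for reading the result.

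SAP 3.2.2 keeps the safety comparison among the primary objectives. SAP 9.1 repeats the descriptive half of the protocol's sentence ("For safety analysis, descriptive statistics will be performed mainly to evaluate the incidence of adverse events and adverse reactions after 12 and 24 weeks") and stops there; the chi-square clause is gone. The ANCOVA and t test in SAP sections 7 and 8 are set out for hemoglobin and other continuous measures, so no test is named for event incidence.

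SAP 9.1 also gives two counting rules. The event tables show the number of patients affected, as a percentage of the population. A later paragraph counts a subject again for each repeat of an event, still over the population size.

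SAP section 5 reports that "finally the study enrolled 43 patients (23 in HEMAX group, and 20 in Eprex/ Erypo® group", against a plan of 60 per arm.

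**The concern.** The efficacy objective has a bound to exclude, 1 g/dl of hemoglobin increase. The safety objective has neither a bound nor an interval. A difference test with nothing beside it gives a reader one fact, whether p fell below a threshold, and a p-value above it becomes easier to obtain as the sample shrinks. Here the sample fell to about a third of the plan (43/120 = 36%).

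The SAP leaves less still: two columns of percentages with no stated uncertainty, and a counting rule under which those percentages may not be the share of patients affected. At stake is whether the report can say, for one of its two primary objectives, how large an excess in adverse-event risk remains compatible with the data.

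**Working it through.** **Is there a plan figure to reproduce?** Not for safety. The only sample-size statement ("A total N of 120 patients (60 in each group) will allow, with 80% of power") concerns hemoglobin and gives no SD, so 120 cannot be re-derived either. The question is what the named test and the two sample sizes can deliver.

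**Inputs**
- Arm sizes: 60 v 60 (Protocol 9.1 and 16.1) and 23 v 20 (SAP section 5).
- Level: two-sided 5%, an assumption. Protocol 16.5 has "using a significance level of 5"%, but in the efficacy section.
- Event rates: assumptions, since the documents give none. Reference rates of 10% to 60% are scanned.

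**Power of the chi-square test.** With a of n1 and c of n2 patients affected, b = n1 − a, d = n2 − c and N = n1 + n2, the uncorrected statistic is X² = N(ad − bc)² / [n1·n2·(a + c)(b + d)], significant above 3.84. Exact power is the sum, over all pairs (a, c) with X² > 3.84, of the product of the two binomial probabilities. Miss rate = 1 − power.

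| Reference v test | Power 60 v 60 | Miss | Power 23 v 20 | Miss |
|---|---|---|---|---|
| 50% v 65% | 0.392 | 61% | 0.163 | 84% |
| 50% v 70% | 0.618 | 38% | 0.259 | 74% |
| 10% v 20% | 0.326 | 67% | 0.115 | 88% |

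Over reference rates of 10% to 60%, exact power by size of excess is:

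| Excess | 60 v 60 | 23 v 20 |
|---|---|---|
| 10 points | 0.205–0.326 | 0.101–0.115 |
| 15 points | 0.392–0.585 | 0.163–0.217 |
| 20 points | 0.612–0.802 | 0.259–0.347 |
| 25 points | 0.803–0.927 at reference rates 10%, 20%, 30%, 40%, 50% and 60% | 0.380–0.491 |

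A continuity correction lowers power further: for 50% v 65%, to 0.322 and 0.100.

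**Interval width.** At equal observed incidence p, the 95% half-width is 1.96·√[p(1 − p)(1/n1 + 1/n2)]. At p = 0.5:
- 60 v 60: 1.96·√(0.25 × 0.03333) = 0.179, about 18 points.
- 23 v 20: 1.96·√(0.25 × 0.09348) = 0.300, about 30 points.

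**What a non-significant result can leave open** (simple Wald intervals, hypothetical counts)
- 40/60 v 30/60: X² = 120 × (40×30 − 20×30)² / (60×60×70×50) = 3.43, not significant. Difference 16.7 points, 95% CI −0.7 to +34.
- 13/23 v 6/20: X² = 43 × (13×14 − 10×6)² / (23×20×19×24) = 3.05, not significant. Difference 26.5 points, 95% CI −2 to +55.

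**Zero counts.** The upper end of the two-sided 95% Clopper-Pearson interval for 0/n is 1 − 0.025^(1/n). For 0/23 this is 14.8%; for 0/20 it is 16.8%.

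**Counting rule.** Suppose 5 of 23 patients each have the same event twice. The patient-level rule gives 5/23 = 21.7%; the repeat-counting rule gives 10/23 = 43.5%. The second figure is not a proportion of patients, so neither a chi-square test nor a risk difference applies to it.

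**The case against.** The strongest reply is that the plan never draws the conclusion being guarded against. Neither document says that p > 0.05 will be taken as comparable safety. The objective is to evaluate and compare incidence, the equivalence claim is confined to hemoglobin and epoetin dose, and the protocol calls the safety analysis mainly descriptive. Under the SAP, which already reports the final enrolment, there is no adverse-event p-value to misread. That stands: the defect is a missing estimate and a missing reading rule, not a wrong inference in the text.

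Two further points stand. The 5% level is not stated for this test. And at the planned size the test is not weak against everything: 20-point excesses are detected with probability 0.61 to 0.80 in the range examined. What counts as a relevant excess is also a judgement that the documents leave open.

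What does not stand is the idea that a descriptive analysis needs no interval. The comparison between arms is a primary objective. Two percentages from 23 and 20 patients do not show their own imprecision, and dropping the chi-square from the SAP removes a weak tool without supplying a better one.

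**Conclusion.** The point holds in limited form. For a stated primary objective, the protocol names only a difference test at an unstated level, the SAP names none, and SAP 9.1 contradicts itself on what is counted. No planned output says what excess in adverse-event risk is excluded. With 43 patients that excess is large: about 30 points either side of the observed difference at 50% incidence, against about 18 points at the planned size. These widths and the miss rates rest on assumed event rates and, for the test, an assumed two-sided 5% level.

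A reader might infer more, and the documents do not support it:
- That the sponsor plans to read non-significance as comparable safety. SAP section 5 does call the conclusions statistically valid despite the smaller number, but in general terms and not about safety.
- That the test misses most relevant excesses at the planned size. It does for 10 points; for 15 points power is 0.39 to 0.59; for 20 points it usually detects them. The statement is fair only at 23 v 20, where power stays below one half for excesses up to 25 points.
- That the chi-square is assigned to antibodies or thromboembolic events. Protocol 16.6 lists these for discussion without naming a test.

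This is worth correcting in the analysis plan. It does not invalidate the safety data.

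**What to change.** In Protocol 16.6 and SAP 9.1:
1. Make the primary safety comparison the risk difference, HEMAX PFS minus EPREX/ERYPO, in the proportion of patients with at least one event, with a two-sided 95% Newcombe or Miettinen-Nurminen interval. Give it at weeks 12 and 24 for any treatment-emergent event and for adverse reactions, and also for serious events, hypertension and thromboembolic events.
2. Report repeat-event counts in a separate table, labelled as events and not as incidence.
3. Give two-sided 95% Clopper-Pearson limits per arm for antibody positivity and for any event with a zero count.
4. Reconcile the two documents on the chi-square: either keep it in both, with its level stated, or drop it from both.
5. State that the safety conclusion will be worded from the confidence interval, and that a non-significant test is not evidence of comparable safety.

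The cost is SAP wording, a few table columns and, for the protocol text, the amendment route in Protocol 17.4. No new data or patients are needed, and no safety margin has to be set. The downside is that at 43 patients the intervals will be wide and the safety conclusion less favourable than bare percentages would suggest.

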17 ETHICAL AND REGULATORY CONSIDERATIONS

17.1 COMPLIANCE WITH THE REGULATIONS APPLICABLE TO CLINICAL TRIALS

The study will be carried out in accordance with the laws, regulations and administrative requirements related to the implementation of Good Clinical Practice in the conduct of clinical trials with medications for human use, as determined by the current national/ local regulations, applicable ANMAT dispositions, the current version of the Declaration of Helsinki and the ICH guidelines.

17.3 INSTITUTIONAL ETHICS COMMITTEE FOR RESEARCH (IECR) / INSTITUTIONAL REVIEW BOARD (IRB)

The study must have written approval from the IECR. Before the beginning of the study, the sponsor or its designee must receive a copy of the letter of approval from the IECR, which will contain the specific identification of the approved documents.

Any relevant amendments to the protocol or subsequent changes in the informed consent form as a

result of the changes in the protocol and/ or Investigator's Brochure approved by the sponsor must also be approved by the IECR and the documentation of this approval will be provided to the sponsor. The records of the IECR review and the approval of all the documents relevant to this study will be kept in the file of the investigator and will be subject to an audit by the sponsor and/ or the regulatory authority during or after study completion. All study documents should be kept for a period of ten years or more according to the current regulations.

In addition, the investigator or sponsor will communicate to the IECR any serious adverse event (SAE) or other according to its regulations.

As needed, periodic reports of the trial progress as well as the notification of study end and a final report, where applicable, will be submitted to the IECR. A copy of all reports submitted to the IECR will also be sent to the sponsor.

17.4 PROTOCOL AMENDMENTS

Protocol changes should only be performed by an approved amendment to the protocol. Protocol amendments must be approved by the sponsor, the IECR of reference and the IECR of each site (if applicable), prior to their implementation.

17.5 CLINICAL STUDY COMPLETION STATEMENT

For all the sites participating in the trial, there will be an end of clinical trial notification to the IECR.

17.6 PATIENT CONFIDENTIALITY

All patient data are identified only by a patient identification number and the existing laws on personal data protection will be respected.

After obtaining the consent from the patient, the investigator will enable the study monitor, the independent auditor or the regulatory agency staff to review the part of the medical history of the patient that is directly related to the study. This will cover all relevant study documentation, including the medical history of the patient, to verify eligibility, summaries of hospitalization/ discharge from any hospitalization that could occur during patient's participation in the study and the reports of autopsies of deaths occurring during the study (if applicable).

17.7 RESPONSIBILITY AND SAFETY

Biosidus Argentina SA will provide a Certificate of Insurance Policy of Clinical Trial to the study sites with the corresponding coverage according to the local current regulations.

18 DOCUMENTATION

18.1 STUDY ARCHIVE AND SITE DOCUMENTATION

Before the start of the study, the following documents must be received by the sponsor from the site:

- 1) Confidentiality Agreement.
- 2) Signed protocol pages, amendments and notifications.
- 3) Curriculum Vitae of the principal investigator and medical license.
- 4) Investigator's statement.
- 5) Clinical Trial Agreement signed.
- 6) Written approval of the IECR for the protocol, amendment(s), informed consent form, patient information sheet (if applicable) and advertising (if applicable).
- 7) List of the IECR members. Committee SOPs.
- 8) Other forms that are applicable according to the local current regulations.

18.2 STUDY DOCUMENTATION PROVIDED BY THE SPONSOR

The sponsor will provide the investigator with the following documents:

- Protocol final version.
- Informed consent (final version).
- Current version of HEMAX PFS package insert project and EPREX/ ERYPO® package insert, which will constitute the product information.
- A printed copy of the ICRF.
- Regulatory document files.
- Certificate of insurance and/ or insurance policy.

